7.3 Optimal Heart Failure Medical Management

To be enrolled into the study, subjects must be receiving stable GDMT for HF per current AHA/ACC guidelines as standard-of-care for HF therapy in the United States and Europe, with any intolerance documented for at least 30 days. This will be verified by the trial specific PROACTIVE-HF Clinical Eligibility Committee. Throughout the study duration, all subjects will continue to receive appropriate medical management for their heart failure, including cardiac medication optimization as well as dietary and fluid restrictions. In addition, subjects will receive Treatment Optimization to target PA pressures, per the Project Specific Guidelines and GDMT considering daily PAP measurements and vital signs collected by Cordella System.

The clinician will contact all subjects on a regular basis to discuss their health status and all patients should be treated according to GDMT.

7.4 Inclusion Criteria

In order to be eligible to participate in this study, each subject must meet all of the following criteria:

1. Subject has given written informed consent

2. Male or female, at least 18 years of age
3. Diagnosis and treatment of HF (regardless of left ventricular ejection fraction (LVEF)) for ≥ 3 months and NYHA Class III HF at time of Screening
4. Subjects should be on stable, optimally titrated medical therapy for at least 30 days, as recommended according to current American Heart Association (AHA)/American College of Cardiology (ACC) guidelines as standard-of-care for HF therapy in the United States, or current European Society of Cardiology (ESC) guidelines for HF treatment in Europe, with any intolerance documented.
5. HF related hospitalization, HF treatment in a hospital day-care setting, or urgent outpatient clinic HF visit for IV diuretics within 12 month (last hospitalization should be 30 days before Screening /Enrollment) **and/or** N-terminal pro-Brain Natriuretic Peptide (NT-proBNP) at time of Screening/ Enrollment defined as:
 - a. Subjects with LVEF $\leq 50\%$: NT-proBNP ≥ 1500 pg/mL.
 - b. Subjects with LVEF $> 50\%$: NT-proBNP ≥ 800 pg/mL.

Thresholds for NT-proBNP (for both LVEF $\leq 50\%$ and LVEF $> 50\%$) will be corrected for body mass index (BMI) using a 4% reduction per BMI unit over 25 kg/m²

6. Subjects should be on diuretic therapy
7. Subjects who are physically able to hold the myCordella™ Patient Reader unit (approximate weight 1.3lb) against the ventral thoracic surface for up to 2 minutes per day while in a seated position, as well as dock and undock the myCordella™ Patient Reader
8. Subjects with sufficient eyesight, hearing, and mental capacity to respond to the myCordella™ Patient Reader's audio/visual cues and operate the myCordella™ Patient Reader
9. Subject has sufficient Cellular and/ or Wi- Fi Internet coverage at home
10. Subject agrees to return to the treating Investigator for all scheduled follow up visits and can return to the hospital for follow up

7.5 Exclusion Criteria

A potential subject who meets any of the following criteria will be excluded from participation in this study:

1. Intolerance to all neuro-hormonal antagonists (i.e., intolerance to ACE-I, ARB, ARNI, and beta-blockers) due to hypotension or renal dysfunction
2. ACC/AHA Stage D refractory HF (including having received or currently receiving pharmacologic circulatory support with inotropes)

3. Subjects with history of recurrent pulmonary embolism (≥ 2 episodes within 5 years prior to Screening Visit) and/or deep vein thrombosis within 3 months of the Screening Visit
4. Subjects who have had a major CV event (e.g., myocardial infarction, stroke) within 3 months of the Screening Visit
5. Unrepaired severe valvular disease
6. Subjects with significant congenital heart disease that has not been repaired and would prevent implantation of the Cordella PA Sensor or mechanical/tissue right heart valve(s)
7. Subjects with known coagulation disorders
8. Subjects with a hypersensitivity or allergy to platelet aggregation inhibitors including aspirin, clopidogrel, prasugrel, and ticagrelor; or patients unable to take dual antiplatelet or anticoagulants for one-month post implant
9. Known history of life threatening allergy to contrast dye.
10. Subjects whereby RHC is contraindicated
11. Subjects with an active infection at the Sensor Implant Visit
12. Subjects with a GFR <25 ml/min or who are on chronic renal dialysis
13. Implanted with CRT-P or CRT-D for less than 90 days prior to screening visit
14. Received or are likely to receive an advanced therapy (e.g., mechanical circulatory support or lung or heart transplant) in the next 12 months
15. Subjects who are pregnant or breastfeeding
16. Subjects who are unwilling or deemed by the Investigator to be unwilling to comply with the study protocol, or subjects with a history of non-compliance
17. Severe illness, other than heart disease, which would limit survival to <1 year
18. Subjects whose clinical condition, in the opinion of the Investigator, makes them an unsuitable candidate for the study
19. Subjects enrolled in another investigational trial with an active Treatment Arm
20. Subject who is in custody by order of an authority or a court of law

7.6 Strategies for Recruitment and Retention

A total of 535 subjects can be enrolled under this clinical protocol/CIP at up to 120 sites in the US and Europe. Potential subjects will be identified by the Investigator and research staff with the study Inclusion and Exclusion criteria in mind. At Screening, subjects will be fully informed on what to expect with study participation to maintain a high study participation retention rate. Subjects will

also undergo a training on the at-home use of the commercial Cordella System to ensure compliance with the web-based clinical care management component of the Cordella™ Heart Failure System, as part of their study screening/ enrollment visit. Throughout the study, subjects will continue to be followed closely to ensure study compliance as well as continued study participation.

7.7 Subject Withdrawal or Termination

7.7.1 Screening Failure and Documentation

Subjects who sign the Informed Consent, but do not meet the inclusion criteria or subjects who meet an exclusion criterion and are not enrolled into the study are considered screening failures. Information on screening failure subjects will be captured on a Screening Failure log and will include demographic information and the primary reasons for Screen Failures will not be recorded in the electronic Case Report Form (eCRF).

7.7.2 Reasons for Withdrawal or Termination

A subject may discontinue his or her participation without giving a reason at any time during the study. Should a subject's participation be discontinued, the primary reason for termination must be recorded in the eCRF. In addition, efforts should be made to perform all procedures scheduled for the Month 6 visit if discontinuation is prior to that visit, or the year 5 visit if discontinuation is after year 4 but before year 5. Subjects who are withdrawn may be replaced with new subjects for evaluation upon Sponsor approval.

The primary reason for discontinuation or withdrawal of the subject from the study should be noted using the following categories:

- Lost to follow-up. The subject did not return to the clinic and attempts to contact the subject were unsuccessful. Attempts to contact the subject must be documented
- Voluntary withdrawal. The subject wishes to withdraw from the study. The reason for withdrawal, if provided, should be recorded in the eCRF. NOTE: All attempts should be made to determine the underlying reason for the withdrawal and, where possible, the primary underlying reason should be recorded
- Principal Investigator withdrawal due to failure to comply with trial requirements or subject is uncooperative or refuses to continue in the trial
- Study termination. The sponsor, IRB/ IEC, or regulatory agency terminates the study
- Other (NOTE: The specific reasons should be recorded in the eCRF)

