6.1 Study Flow

The study will implant up to 535 subjects. Assuming a dropout rate of approximately 10% by 6 months, this study will implant a maximum of 450 patients in Cohort #2 and Cohort #3. This is to achieve at least 406 implanted patients with complete follow-up at 6 months. After completion of enrollment and as soon all 406 subjects reach their 6 month follow- up visit, the 6 month primary endpoint data will be used for Premarket Approval (PMA) submission. Up to 85 subjects (cross- over from former **Control Arm**) will continued to be followed in Cohort #1.

[figure not shown]

Figure 9: Study Flow

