8.1.19 Cordella PA Sensor and HF System Data Transmission & Compliance

All subjects will be instructed to transmit their clinical data daily (PAP data and vital signs) using the myCordella™ Tablet during the study. Subjects will be asked to transmit their clinical data at approximately the same time each day (typically in the morning). Subjects will also be given a pre-set time window to make their daily transmission.

Use of the Cordella System and PAP Measurements will be monitored, and compliance will be measured by tracking the number of transmitted data occurrences. For study purposes, compliance will be defined as subjects transmitting at least 5 days of myCordella™ clinical data per week (does not need to be consecutive days). If a subject does not transmit at least 5 days per week, Endotronix will notify the study site on a regular basis on their subject’s compliance.

Subjects will then be notified by the study site to review system use expectations and any other user issues will be addressed.

To help subjects with data transmission compliance during the study, the myCordella™ Tablet will be programmed with daily reminders to transmit data, successful transmission indicators, and flags to transmit data if a transmission is missed.

8.1.20 myCordella™ Patient Management Portal (PMP) Data Review and Contact

Following the Cordella PA Sensor implant, clinical data from the Cordella™ Heart Failure System including PAP sensor data will be continuously transmitted by all subjects and monitored by clinicians at the study site. Clinicians will be trained by an Endotronix representative on how to use the myCordella™ PMP to review data transmissions.

For all subjects’ mandatory reviews and acknowledgements of all subject’s vital signs is required as per the table below to assure optimal hemodynamic PAPGHFM in addition to GDMT HF management for all patients:

Data Review Schedule		Comments
Recommended Cordella System	At least 2 times per week	
Mandatory PAP Sensor Data	2 times per week	maximum of 4 days between data reviews

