9 ADVERSE EVENTS

From the time of enrollment, at each evaluation of a subject enrolled in the trial, the investigator or site staff determines whether any adverse events (AE) have occurred and determines their relationship to the study devices or procedures. All adverse events, study device malfunctions and other product issues must be recorded in the appropriate eCRF section(s).

Safety will be assessed throughout the study by the frequency of Adverse Events (AEs), pressure sensor failure rate, and device/system-related complications by relationship to the device and severity. Additional emphasis on safety for the primary safety endpoint will be placed through 6 month following the Cordella PA Sensor Implant procedure to capture any adverse events associated with use of the Cordella PA Sensor.

Adverse events may be volunteered spontaneously by the subject, or discovered as a result of general, non-leading questioning. If it is determined that an AE has occurred, the investigator should obtain all the information required to complete the AE page of the eCRF, in accordance with the guidelines that accompany it. The investigator must submit to sponsor (or designee) any UADEs, and SAEs occurring during the study within 24 hours after being notified of the event and provides additional information, if required by Endotronic.

All AEs must be followed until resolution, until the condition stabilizes, until the event is otherwise explained or is judged by the investigator to be no longer clinically significant, or until the subject is lost to follow-up. The investigator is responsible for ensuring that follow-up includes any supplemental investigations necessary to elucidate as completely as practical the nature and/or causality of the AE. This may include additional laboratory tests or investigations, histopathological examinations, or consultation with other health care professionals.

Investigators are not obligated to actively seek AEs in former study participants. However, if the investigator learns of any SAE, including a death, at any time after a subject has been discharged from the study, and he/she considers the event reasonably related to the investigational product or study participation, the investigator should promptly notify Endotronic.

All AEs will be collected until a subject's participation in the trial is considered complete.

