A subject may discontinue his or her participation without giving a reason at any time during the study. Should a subject's participation be discontinued, the primary reason for termination has to be recorded in the Electronic Case Report Form (eCRF). In addition, efforts have to be made to perform all procedures scheduled for the Month 6 (V5) visit if discontinuation is prior to that visit, or the year 3 (V9) visit if discontinuation is after year 2 but before Year 3. Subjects who are withdrawn may be replaced with new subjects for evaluation upon Sponsor approval.

The primary reason for discontinuation or withdrawal of the subject from the study is collected using the following categories:

- Lost to follow-up. The subject did not return to the clinic and attempts to contact the subject were unsuccessful.
- Voluntary withdrawal. The subject wishes to withdraw from the study. The reason for withdrawal, if provided, recorded in the eCRF.
- Principal Investigator withdrawal due to failure to comply with trial requirements or subject is uncooperative or refuses to continue in the trial
- Study termination. The sponsor, Institutional Review Board (IRB), or regulatory agency terminates the study
- Other

After completion of the last study visit (V9) the subject continues to participate in the site-specific Heart Failure Follow-up program.

Main analysis to demonstrate durability of the treatment effect is planned to be performed at the timepoint, when all Cohort #2 and #3 subjects have completed 6 months of follow-up or discontinued study earlier. At this timepoint the complete analysis as defined in the SAP will be performed, including definition of the protocol deviations and analysis sets. The analysis will be done on the clean and coded data.

Once all subjects completed the final study visit (V9) or terminated early from the study, a follow-up analysis will be done. For the follow-up analysis, the complete set of outputs will be refreshed based on the data available at study end.

DSMB meetings are planned for the study and will follow the scheduled defined in the DSMB charter.

This document is confidential.

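### Withdrawal of an implanted subject for non-compliance ends event follow-up, so the HF hospitalisation/death rate is biased low if later risk is higher, by an amount the plan leaves unknown

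*Protocol*

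**What the plan says.** - **Reason for leaving.** Protocol 7.7.2 lists "Principal Investigator withdrawal due to failure to comply with trial requirements or subject is uncooperative or refuses to continue in the trial" among the categories for discontinuation. SAP 2.2 repeats it: "Principal Investigator withdrawal due to failure to comply with trial requirements".
- **What is attempted at withdrawal.** The same protocol section says "efforts should be made to perform all procedures scheduled for the Month 6 visit if discontinuation is prior to that visit". Those procedures include subject status and adverse events (Protocol 8.3.5). Protocol 8.3.9 describes one early termination visit.
- **After withdrawal.** Protocol 9 says "All AEs will be collected until a subject's participation in the trial is considered complete", and "Investigators are not obligated to actively seek AEs in former study participants". An SAE or death that the investigator happens to learn of later is to be notified only if it is judged reasonably related to the device or the study.
- **Analysis.** The mITT holds all implanted Cohort #2 and #3 subjects (Protocol 10.2.3, SAP 4.3). SAP 7.1.1 ends exposure at death, early discontinuation or 180 days. SAP 5.2 instead uses the last date available for withdrawn subjects. Protocol 10.8 and SAP 5.3 treat censoring as sufficient handling of dropout.
- **Sensitivity.** Protocol 10.8 promises missing-data sensitivity analyses. SAP 8.1.2 specifies them (extreme cases, tipping point) for the primary safety endpoints only. Primary efficacy gets a negative binomial model (SAP 7.1.2).
- **Replacement.** Protocol 7.7.2 adds "Subjects who are withdrawn may be replaced with new subjects for evaluation upon Sponsor approval".

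**The concern.** The plan does not separate failing to comply from leaving event follow-up. Vital status and hospital admissions can be learned without any device reading, so losing them for a non-compliant implanted subject is avoidable.

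Censoring at withdrawal leaves the rate unbiased only if the later event rate equals the rate on study. Withdrawal for poor compliance may well be related to prognosis. Protocol 1.3 itself argues that raised pressure left untreated tends to end in decompensation and readmission, which points to a higher later rate, although no document gives a figure.

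The trial is open-label and single-arm. It is judged against a fixed goal of 0.43 and an observed-rate limit of 0.37, and there is no control arm in which the same loss could offset it. The same rule governs the gated 12-month endpoint (goal 0.70, limit 0.59). No planned efficacy analysis tests the censoring assumption: a negative binomial model allows for overdispersion, not for informative dropout.

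**Working it through.** **Inputs from the documents.** 450 implanted and 406 evaluable, so 450 − 406 = 44 planned non-completers; goal 0.43; one-sided alpha 0.025; planned rate 0.34; observed-rate limit 0.37 (Protocol 6.1 and 10.3).

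**Assumed, because the documents do not say.** Number withdrawn *w* = 11, 22 or 44; withdrawal on average at mid-window, so lost time is L = w/2 subject-half-years; rate ratio *k* after withdrawal against before.

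**1. The plan's own figure.** One-sample Poisson power at n = 406:
Φ[(√406 × (0.43 − 0.34) − 1.96 × √0.43) / √0.34] = Φ(0.906) = 81.8%. The exact Poisson calculation (success with at most 148 events) gives 81.4%. The stated figure of more than 80% reproduces.

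**2. Rate ratio at which an observed rate r becomes 0.37 on full follow-up.**
Full-follow-up rate = r × [(450 − L) + L × k] / 450, so k = 1 + 450 × (0.37 − r) / (L × r).

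| Withdrawn | L | k for r = 0.36 | k for r = 0.34 |
|---|---|---|---|
| 11 | 5.5 | 1 + 4.5/1.98 = 3.3 | 1 + 13.5/1.87 = 8.2 |
| 22 | 11 | 1 + 4.5/3.96 = 2.1 | 1 + 13.5/3.74 = 4.6 |
| 44 | 22 | 1 + 4.5/7.92 = 1.6 | 1 + 13.5/7.48 = 2.8 |

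If 20 of the 44 were deaths, 24 live withdrawals remain, L = 12 and k for r = 0.36 is 1 + 4.5/4.32 = 2.0.

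An observed 0.36 over 450 − 22 = 428 half-years (about 154 events) has an upper bound near 0.42, so it passes both success conditions as the plan stands.

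**3. Chance of declaring success when the true full-follow-up rate is exactly 0.43** (both conditions applied, later time censored):

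| Withdrawn | k = 1 | k = 1.5 | k = 2 | k = 3 |
|---|---|---|---|---|
| 11 | 2.5% | 3.0% | 3.6% | 5.1% |
| 22 | 2.2% | 3.1% | 4.5% | 8.2% |
| 44 | 2.3% | 4.7% | 8.6% | 21.8% |

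At k = 1 there is no inflation over the nominal 2.5%.

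**4. Unseen events needed to overturn a pass.** On full follow-up of 450 subjects, at most 166 events pass. The largest passing counts with censoring are 164, 161 and 157 for 11, 22 and 44 withdrawn, so a bare pass fails with 3, 6 or 10 unseen events. At the planned rate with 44 withdrawn (0.34 × 428 ≈ 146 events), 167 − 146 = 21 unseen events are needed.

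**The case against.** The other side has a good deal to say, and most of it limits the point rather than removing it.

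- A reader might infer that withdrawn subjects vanish from the mITT. They do not: all events and time up to withdrawal count. Only later events and later time are missing.
- A reader might infer that subjects are removed because they stop using the device. No section makes missed readings a trigger for withdrawal. Protocol 8.1.19 does define compliance as transmitting on at least 5 days a week, so 7.7.2 could reach such subjects. Its stated response, though, is notification and counselling: "If a subject does not transmit at least 5 days per week, Endotronix will notify the study site".
- Sites must try to perform the Month 6 procedures. That is a real mitigation, but only an effort, with no timing, and SAP 7.1.1 has already closed exposure.
- A reader might see the replacement sentence as breaking "this study will implant a maximum of 450 patients in Cohort #2 and Cohort #3", or as a way to discard poor performers. Neither follows. Enrolment precedes implant, so replacing someone withdrawn before implant does not touch the cap, and neither does replacement while fewer than 450 are implanted. A replaced implanted subject's recorded events stay in the mITT.
- The 44 would also include loss to follow-up, voluntary withdrawal and perhaps deaths. Treating all of them as investigator withdrawals gives an upper bound, not an estimate, and a result near 0.34 is fairly robust.

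What still stands: there is no duty to find out about deaths or HF admissions after discontinuation, exposure is closed there, and no efficacy analysis tests the consequence.

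**Conclusion.** The point holds as an avoidable source of informative censoring, not as an error in any stated figure. The 6-month and 12-month rates are biased low if risk after withdrawal for non-compliance exceeds risk on study, and not otherwise.

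The size cannot be fixed from the documents, because they give neither the number withdrawn for this reason nor the later rate. Under mid-window withdrawal, an observed 0.36 reaches 0.37 at a ratio between about 3.3 (11 withdrawn) and about 1.6 (44, the upper bound). From the planned 0.34 the ratios are 8.2 and 2.8. It matters mainly if the result lands close to the limit. The change is worth making because it is cheap, with medium confidence that the bias would be material.

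**What to change.** 1. **Protocol 7.7.2.** Do not let non-compliance alone end study follow-up of an implanted subject. Record it as a deviation and deal with it through the Per Protocol set, which already exists for that purpose.
2. **Ascertainment.** Unless consent for follow-up is withdrawn, establish vital status and HF hospitalisations by phone or record review to day 180 and day 365. Count those events and that exposure in the mITT.
3. **SAP exposure.** Reconcile 5.2 with 7.1.1 by ending exposure at the last date on which event status was actually known, so that counted events and counted time cover the same period.
4. **SAP sensitivity.** Add a tipping-point analysis for the primary efficacy endpoint, as Protocol 10.8 leads one to expect.
5. **Replacement.** State whether the sentence applies to implanted subjects, and that any replaced implanted subject remains in the mITT.

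**Cost.** A protocol and SAP amendment and a few phone or record checks. Protocol 6.3 estimated the last implant for the first quarter of 2023 and the latest amendment is dated November 2023, so the 6-month checks may have to be retrospective. The event rate may come out less favourable.
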